4.1 Inclusion Criteria

1. Written Informed Consent given by the patient or, if not possible, by a legally authorized representative and/or an independent physician as authorized by the competent ethics committee (EC) or independent review board (IRB) and local regulations.

2. To be at least 18 years of age.

For Taiwan: To be at least 20 years of age.

South Korea only: To be at least 19 years of age.

3. To be treated in an ICU at the time of enrollment.

4. Endotracheal tube in place (tracheostomy is allowed).

5. The patient is mechanically ventilated.

6. Diagnosis of pneumonia based on the following criteria (a, b, c, all must be met):

a. One definitive chest X-ray diagnostic of pneumonia,

or

A sequence of at least 2 chest X-rays showing the presence of new or progressive infiltrate(s) suggestive of bacterial pneumonia.

b. Hypoxemia based on at least one of the following measurements/criteria:

i. $\text{PaO}_2/\text{FiO}_2 < 250$ mmHg (at sea level or equivalent for significant elevations above sea level) while intubated and mechanically ventilated, as one or more measures within ≤ 24 hours prior to randomization, or

ii. $\text{PaO}_2 < 60$ mmHg (at sea level or equivalent for significant elevations above sea level) while intubated and mechanically ventilated, as one or more measures within ≤ 24 hours prior to randomization), or

iii. Respiratory failure necessitating intubation and mechanical ventilation. If tracheostomy is in place, the need for mechanical ventilation.

c. At least one of the following signs:

i. Documented fever (e.g., body temperature greater than or equal to 38° Celsius).

ii. Hypothermia (e.g., core body temperature less than or equal to 35° Celsius).

iii. Total peripheral white blood cell (WBC) count greater than or equal to 10,000 cells/ μL (or mm^3).

iv. Leukopenia with total WBC less than or equal to 4,500 cells/ μL (mm^3).

v. Greater than 15 percent immature neutrophils (bands) noted on peripheral blood smear.

7. Documented pulmonary infection with *P. aeruginosa* obtained by BAL, mini-BAL, protected ETA (collectively ‘airway specimen’). For the study randomization, *P. aeruginosa* must be identified by one of the three methods below:
 - a. An airway specimen culture positive by any method for *P. aeruginosa* of a specimen obtained less than 72 hours prior to randomization. A fresh airway specimen must be obtained prior to treatment initiation for standard microbial culture by the local laboratory (including organism identification, quantitative/semi-quantitative culture and susceptibility testing); the corresponding culture results are NOT required prior to randomization.

OR
 - b. A rapid diagnostic test (see section 14.3 for acceptable methods). In such case, the same sample must ALSO be used for standard microbial culture by the local laboratory (including organism identification, quantitative/semi-quantitative culture and susceptibility testing). The corresponding culture results are NOT required prior to randomization.

OR
 - c. A positive airway specimen culture by any method of *P. aeruginosa* from a specimen obtained at screening (quantitative, semi-quantitative).
8. APACHE II score ≥ 10 and ≤ 35 within 24 hours once subject has consented.

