1.5.2 Risks related to the study design and required procedures

Aerucin® will be administered in addition to standard-of-care antibiotic therapy, as determined by the investigator on the exclusive basis of the medical needs of his/her patient. Therefore, participation in this study does not affect the chances of a positive clinical outcome in any given study subject, also taking into account the favorable safety profile of the investigational product.

Except for blood sampling for PK and anti-drug antibody (ADA), and rapid testing of airway specimens for assessing the presence of *P. aeruginosa*, the procedures that are required for the study are all routine procedures, in nature and frequency, for this type of patients whose clinical status requires hospitalization in an ICU. Therefore, with the exceptions noted earlier, this study does not impose an unreasonable burden on the study subjects.

Blood sampling for PK and ADA has been reduced to the minimum necessary by allowing sparse sampling for the majority of the study subjects, on the one hand, and by limiting the required sample volume to the minimum technically necessary for the assays, thus limiting the related burden as much as possible.

Eligible study subjects will be randomized and treated either on the basis of culture results (known from recent cultures) or on the basis of rapid diagnostic testing of airway specimens using devices such as CE marked Cepheid's GeneXpert® with Investigational / Research Use Only (IUO / RUO) PA Cartridge, BioFire Diagnostics, LLC (a BioMerieux company)'s IUO FilmArray® LRTI Panel (please refer to section 14.3). This approach is necessary to allow the study intervention to be implemented as early as possible in the course of the disease, as early treatment is a known driver of clinical outcomes. It is expected that the results of rapid testing will not be confirmed by standard microbial culture in a small number of subjects for various reasons including the possibility of rapid test false positive, inadequate samples, or sample cultures affected by an ongoing antibiotic treatment. This situation is not expected to occur in more than 5% of the randomized subjects. Considering the safety profile of Aerucin® and of similar fully human anti-infective mAbs, this risk is deemed acceptable in the context of this study protocol.

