5.3 Randomization and Blinding

This is a double-blind, placebo-controlled study.

Study subjects will be first stratified as follows:

- Stratum 1: VABP or non-VABP
- Stratum 2: PaO₂/FiO₂ ≤200 or >200
- Stratum 3: Americas, Eastern EU, Western EU and Asia

Randomization will proceed in a 1:1 ratio, in blocks of 4, for the study overall.

A computer-generated randomization schedule will be used to allocate study treatment according to the above randomization scheme. Upon confirmation of eligibility, the study personnel will be prompted to randomize the study subject using the electronic data capture (EDC) / interactive web-based randomization system (IWRS) system.

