9.3 Statistical Methods

Continuous data will be summarized by means, standard deviations, median, min, and max. Categorical data will be summarized by frequency and percentages.

The primary endpoint of Clinical Cure rate at Day 21 will be analyzed using a stratified Cochran-Mantel-Haenszel (CMH) test. The CMH test will be stratified by baseline randomization strata. Time to Clinical Cure will be analyzed using a stratified log rank test. Other continuous endpoints will be analyzed using an Analysis of Covariance (ANCOVA), with treatment as a main effect, site, and baseline strata as covariates. Treatment by site interaction will be evaluated separately. Secondary endpoints will be analyzed using a sequential procedure in predefined order. Categorical variables will be analyzed using a stratified CMH test.

The primary comparisons for all endpoints will be between the 20 mg/kg dose group and placebo and will be done at 0.05 level of significance. The details of the planned analyses will be provided in the Statistical Analysis Plan.

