14 APPENDIX B: OTHER TRIAL SPECIFIC PROCEDURES

14.1 APACHE II Score

The score computed by the study site according to standard practice will be entered in the EDC system. The corresponding worksheet, including all the data that were used to compute the recorded score, will be stored as source data in the site study files.

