#### **6.3.3. Demographic and Baseline Characteristics**

The following demographic and baseline characteristics will be summarized:

- Age (years) and age categories (<65 years or ≥65 years);
- Sex;
- Race;
- Ethnicity;
- Height (cm);
- Weight (kg);
- Body mass index (BMI) (kg/m^2) ;
- Randomization stratum 1: VABP or non-VABP;
- Randomization stratum 2: PaO2/FiO2 ≤200 or >200;
- Randomization stratum 3: Americas, Eastern EU, Western EU or Asia;
- Baseline APACHE score: ≥20 and <20;
- Baseline pathogen status: Monopathogen (*P. aeruginosa* only) or Multiple pathogens in baseline culture;
- Baseline pathogen susceptibility for *P. aeruginosa*: Multi Drug Resistant (MDR) or Susceptible for *P. aeruginosa*;
- Reason for admission to ICU at baseline (Trauma or Non-trauma);
- Randomization confirmed method: Rapid test only or Culture confirmed randomization; and
- Time from Pneumonia Diagnosis (days).

Demographic and baseline characteristics will be summarized with descriptive statistics or counts and percentages of subjects as appropriate by treatment group and in total for the ITT, micro-ITT, and PP Populations.

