##### **6.4.2.2. Mortality**

All-cause mortality and pneumonia-related mortality rate by Day 7, 14, 21, and 28 will be tabulated by treatment group for the micro-ITT Population and analyzed using a stratified CMH test based on the stratification factors at randomization. The P-value from the stratified CMH test will be presented. In addition, plots of the Kaplan-Meier estimate of the survival distribution function over time will be presented by treatment group.

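### Cure and mortality are tested by CMH on the randomization strata alone; the APACHE II score recorded for every subject enters no model, at a modest cost in precision

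*Protocol*

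**What the plan says.** Protocol 4.1, criterion 8, requires "APACHE II score ≥ 10 and ≤ 35 within 24 hours once subject has consented". Protocol 14.1 makes it a numeric database item: "The score computed by the study site according to standard practice will be entered in the EDC system". Table 6-1 and Protocol 6.3 place it at Day -1, before dosing.

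For the primary endpoint, Protocol 9.3 states: "The CMH test will be stratified by baseline randomization strata". SAP 6.4.1.1 repeats this and names VABP status, PaO2/FiO2 (cut at 200) and region. Protocol 5.3 gives region four levels ("Stratum 3: Americas, Eastern EU, Western EU and Asia"). SAP 6.4.2.1 uses a stratified CMH test for cure at Days 7, 14 and 28. Under SAP 6.4.2.2, all-cause and pneumonia-related mortality are "analyzed using a stratified CMH test based on the stratification factors at randomization".

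APACHE II is used in two places. It is a dichotomized baseline characteristic ("Baseline APACHE score: ≥20 and <20", SAP 6.3.3) and a subgroup factor with the same cut (SAP 6.4.4). That subgroup analysis is optional for Day 21 cure but stated as definite for Days 7, 14 and 28. None of the sensitivity analyses in SAP 6.4.1.1 adjusts for it.

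**The concern.** The entry range spans 25 APACHE II points, so subjects will differ widely in severity. If the score predicts cure or death, leaving it out costs precision. It also leaves the result exposed to whatever difference in severity chance puts between two arms of about 70 to 77 subjects. Should such a difference appear in the baseline table, no prespecified analysis would address it, and any adjustment added later would be open to challenge.

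SAP 6.4.1.1 also allows strata to be merged, or the CMH test replaced by, for example, Fisher's exact test, if cells are too small. That could remove even the PaO2/FiO2 adjustment. The plan promises only a P-value from the primary test, so an adjusted analysis would also supply an effect estimate with an interval.

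**Working it through.** **1. The plan's own power figure.** Inputs (Protocol 9.2, SAP 4): 65% vs 85% cure, 69 per arm, two-sided 0.05, Fisher's exact test. Exact enumeration over the two binomials gives 73.3%, against the stated figure of more than 90%. The uncorrected chi-square test gives 78.1%. At 77 per arm the figures are 78.3% and 82.4%. The dropout step does reproduce: 69 / 0.9 = 76.7, so 77 per arm and 154 in total. The trial therefore has less power to spare than it states.

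**2. Number of CMH cells.** 2 x 2 x 4 = 16. With 138 subjects that is 138 / 16 = 8.6 per cell on average.

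**3. Power for Day 21 cure.** Simulation used 1:1 blocks of 4 within 16 strata and marginal cure of 65% vs 85%. Assumptions not in the documents:
- APACHE II normal (mean 20, SD 6) truncated to 10-35, giving mean 20.5 and SD 5.26;
- stratum shares;
- strata neither prognostic nor related to APACHE II;
- the strength of APACHE II.

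The middle model, strata as main effects without APACHE II, separates the two sources of gain.

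N = 138, logistic score tests, 4000 runs per row (Monte Carlo SE about sqrt(0.8 x 0.2 / 4000) = 0.6 points):

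| OR per SD | 16-cell CMH | Strata main effects | Plus APACHE II | Due to APACHE II |
|---|---|---|---|---|
| 1.0 | 78.7% | 80.7% | 80.4% | -0.3 |
| 1.5 | 78.0% | 80.1% | 80.7% | +0.6 |
| 2.0 | 78.7% | 80.5% | 83.7% | +3.2 |
| 2.5 | 79.7% | 81.4% | 86.0% | +4.6 |
| 3.0 | 78.3% | 80.8% | 87.4% | +6.6 |

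N = 146 (154 less the 5% of unconfirmed rapid tests that Protocol 1.5.2 gives as its upper expectation: 154 x 0.95 = 146.3). Here strength is set as log-odds per point. OR per SD = exp(5.26 x slope size), so -0.08, -0.12 and -0.17 correspond to about 1.5, 1.9 and 2.4. CMH power is about 80% and strata main effects about 81%. With APACHE II, power is 81%, 83%, 84% and 87% at slopes 0, -0.08, -0.12 and -0.17. The score itself adds about 0, 2, 3 and 6 points.

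N = 154: CMH 81-83%, with APACHE II 84-89%. No scenario reaches 90%.

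**4. Type I error.** At N = 138 (3000 runs, Monte Carlo SE about 0.4 points) null rejection was 4.5-6.2% for CMH, 5.0-6.8% for strata main effects and 5.1-6.6% with APACHE II. There was no consistent difference between the last two.

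**5. Chance imbalance.** The SE of the arm difference in mean APACHE II, in SD units, is sqrt(2/69) = 0.170. The 95% limit is 1.96 x 0.170 = 0.33 SD, or about 1.8 points at an SD of 5.3. If half of subjects score 20 or more, the SE of the difference in proportions is sqrt(2 x 0.25 / 69) = 0.085. The chance of a gap above 10 percentage points is then 24%.

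With no treatment effect and an imbalance of 0.33 SD, simulation gives:

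| OR per SD | Mean spurious cure difference (points) | Conditional type I error, CMH | Same, APACHE II in model |
|---|---|---|---|
| 1.5 | 2.7 | 5.4% | 5.1% |
| 2.0 | 4.7 | 7.4% | 5.2% |
| 3.0 | 6.7 | 10.3% | 5.2% |

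**6. Mortality.** The documents give no design rate, so 30% vs 15% is assumed. At N = 138, CMH power is 55%. With APACHE II it is 58%, 62% and 65% at OR 1.5, 2 and 3 per SD, of which about 2 to 3 points come from leaving the 16-cell CMH.

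**The case against.** The strongest reply is that nothing here is an error. CMH on the randomization strata is a valid test of a randomized comparison, and it already includes a severity marker: Protocol 6.3 defines severe disease as PaO2/FiO2 of 200 or below, which is both a randomization and an analysis stratum. A reader might infer that the treatment comparison is biased, or that severity goes wholly uncorrected. The documents support neither. Averaged over randomizations, CMH keeps its error rate; what is lost is precision and control conditional on an observed imbalance.

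The second reply is that part of the apparent gain has nothing to do with APACHE II. That stands: in another run at N = 146, a score with no prognostic value went with 83.2% power against 80.1% for CMH, because the 16-cell test had been replaced. The simulation also makes the strata unrelated to APACHE II, which may overstate what the score adds beyond PaO2/FiO2.

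A third reply is that the standardized estimator is a slightly looser test. In that same run its null rejection was 5.6-6.6%, against 4.7-5.5% for CMH. This does not explain the APACHE II increment, which is measured between two versions of one model with similar null rejection. It is a reason to keep CMH as the primary test if the sponsor prefers.

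Two further inferences are tempting. One is that criterion 8, being tied to consent, yields a score out of date at dosing. Table 6-1 and Protocol 6.3 put the score at Day -1 as a baseline assessment, followed by prompt randomization and treatment, so this is at most loose wording. The other is that time from diagnosis must also be modelled, because Protocol 1.5.2 justifies rapid testing "as early treatment is a known driver of clinical outcomes". Its benefit as a covariate was not quantified.

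**Conclusion.** The point holds as a missed improvement in precision. CMH on the randomization strata is the only planned test of cure and mortality, and a score available for every subject before dosing enters no model.

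For slopes of 0 to -0.17 per point, APACHE II itself is worth about 0 to 6 points of power for Day 21 cure. It is negligible at an OR of 1.5 per SD and about 3 points at an OR near 2. Replacing the 16-cell CMH with main effects is worth a further 1 to 3 points, and type I error stays at about 5-6%. Protection against chance imbalance matters only if the score is at least moderately prognostic.

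All of this rests on an assumed prognostic strength and APACHE II distribution. It should not be read as a way to recover the stated power: no scenario reached 90%, and that figure does not reproduce by the plan's own method.

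**What to change.** Before unblinding, add to SAP 6.4.1.1 a covariate-adjusted analysis of Day 21 cure in the micro-ITT population: a logistic model with treatment, the three randomization factors as main effects and baseline APACHE II as a continuous term, reported as a standardized risk difference with a 95% CI. Name it as the first sensitivity analysis, or as primary if the sponsor prefers. Apply the same model to cure at Days 7, 14 and 28 (SAP 6.4.2.1) and to all-cause mortality (SAP 6.4.2.2). Time from pneumonia diagnosis may be added as an option.

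The cost is a paragraph of SAP text and one model, with no new data. The small downside is reliance on a working model. No change to criterion 8 is needed for this purpose; at most its timing wording should be reconciled with Table 6-1 and Protocol 6.3.

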4.2 Exclusion Criteria

1. The subject is moribund. Clinical judgment by the investigator that the subject is unlikely to survive the current illness/ICU-admission/treatment period despite delivery of adequate antibiotics for treatment of *P. aeruginosa* pneumonia.
2. Effective antibacterial drug therapy for the index pneumonia administered continuously for 48 hours or more prior to initiation of study treatment. Effective antibiotics would include those typically used to treat *P. aeruginosa*.
3. Plasmapheresis (ongoing or planned) or any procedure that would remove/filter out the monoclonal antibody/study drug.
4. Immunocompromised and at risk of infection by opportunistic pathogens including, but not limited to the following:
 - a. HIV / AIDS who are not stable under medication and/or most recent CD4 < 200.
 - b. Expected neutropenia due to chemotherapy.
 - c. Absolute neutrophil count less than 500/ μ L (mm^3).
 - d. Heart or lung transplant recipient within the past 6 months.
5. Known hereditary complement deficiency.
6. Liver dysfunction with a Child Pugh C score (Child Pugh score of A or B are acceptable at discretion of the Principal Investigator [PI]).

7. Pulmonary disease that precludes evaluation of a therapeutic response (such as lung cancer resulting in bronchial obstruction or on the same side as the pneumonia, active tuberculosis, cystic fibrosis, granulomatous disease, fungal pulmonary infection, lung abscess, pleural empyema or post obstructive pneumonia).
8. Patient has received intravenous (IV) immunoglobulin therapy within 3 months prior to the Screening Visit.
9. Any woman of child-bearing potential (WOCBP) who does not have a negative pregnancy test result at Screening using SERUM or URINE testing based on Beta-subunit human chorionic gonadotropin (HCG) standard tests and methods from the local laboratory. Non-pregnant and non-lactating with confirmation via local laboratory testing is required. Women who are post-menopausal as evidenced by the absence of menstruation for at least 1 year are eligible; the date of last menstruation is to be recorded in the study files unless post-menopausal status is obvious due to age.
10. Any sexually active subjects who is unwilling to use acceptable methods of contraception for 120 days after dosing. WOCBP must agree to use to an effective method of birth control (e.g., prescription oral contraceptives, contraceptive injections, contraceptive patch, intrauterine device, barrier methods, abstinence) or male partner sterilization alone for the duration of the study and for at least 120 days after dosing. Males with female partners of reproductive potential must agree to practice abstinence or to use a condom (male) plus an additional barrier method (female partner) of contraception for the duration of the study and for at least 120 days after dosing.
11. Known lack of treatment compliance from prior studies or ongoing medical care based on medical records and PI's judgment and/or the capacity of the patient to comply with all study requirements.
12. Any medical, psychological, cognitive, social or legal conditions that would interfere in the ability to give an Informed Consent OR the absence of a legally valid representative of the patient or independent physician allowed and able to give consent on his/her behalf.
13. Participation as subject in another interventional study within 30 days prior to the first dose of study treatment, or planned participation in such a study during the study or within 30 days of its completion by the patient. Patients who participate in observational or epidemiological studies are also eligible provided this does not interfere with their capacity or the capacity of the study staff to comply with all study requirements.

4.3 Withdrawal Criteria

Participation of a subject in this clinical study may be discontinued, but not limited to, any of the following reasons:

- The subject withdraws consent or formally requests discontinuation from the study for any reason;
- The subject is lost to follow-up
- Improvement of pneumonia and discharge from ICU should NOT be considered withdrawal. All assessments including Clinical Cure assessment should be collected through Day 28

- Termination of the study by the Sponsor or the regulatory authority.

If a subject withdraws prematurely from the study due to the above criteria or any other reason, study staff should ensure that End of Study Visit data are recorded. The reason for subject withdrawal must be documented in the electronic case report form (eCRF).

In the case of subjects lost to follow-up, attempts to contact the subject must be made and documented in the subject's medical records, including whether the subject is alive at the time of contact.

Withdrawn subjects will not be replaced.

5 STUDY TREATMENTS

5.1 Treatment Groups

After completing all screening procedures, eligible study subjects will be randomized to one of the following treatment groups:

- Control group: placebo
- Investigational Product group: Aerucin® 20 mg/kg

5.2 Rationale for Dosing

Aerucin® was shown to be safe when administered in doses up to 20 mg/kg intravenously over 1 hour in a phase 1 safety and PK study of 16 healthy volunteers. The 20 mg/kg dose, the highest dose then tested, was selected for this study because of the existence of a dose-response in animal studies, because of the severity of the target infection, and because the target for Aerucin® is specific to *P. aeruginosa*, the amount of which may affect the PK profile of the product.

5.3 Randomization and Blinding

This is a double-blind, placebo-controlled study.

Study subjects will be first stratified as follows:

- Stratum 1: VABP or non-VABP
- Stratum 2: PaO₂/FiO₂ ≤200 or >200
- Stratum 3: Americas, Eastern EU, Western EU and Asia

Randomization will proceed in a 1:1 ratio, in blocks of 4, for the study overall.

A computer-generated randomization schedule will be used to allocate study treatment according to the above randomization scheme. Upon confirmation of eligibility, the study personnel will be prompted to randomize the study subject using the electronic data capture (EDC) / interactive web-based randomization system (IWRS) system.

